14.1 Safety profile of the procedure

Safety evaluation will focus on potential adverse events (AEs) related to the biopsy procedure, since no investigational drug or device is used in this study.

14.2 Adverse Event Definitions

Adverse Event (AE)	Any untoward medical occurrence in a patient or clinical investigation subject treated with the investigational treatment and which does not necessarily have a causal relationship with this treatment. An adverse event (AE) can therefore be any unfavorable and unintended sign (including an abnormal laboratory finding), symptom, or disease temporally associated with the treatment, whether or not related to the treatment. Reference: adapted from GCP ICH E6(R2)
Serious Adverse Event (SAE)	Any untoward medical occurrence that at any dose: – results in death, – is life-threatening, – requires inpatient hospitalization or prolongation of existing hospitalization, – results in persistent or significant disability/incapacity, or – is a congenital anomaly/birth defect. Reference: GCP ICH E6(R2)
Adverse Event of Special Interest AESI	An adverse event of special interest (serious or non-serious) is one of scientific and medical concern specific to the sponsor's product or program, for which ongoing monitoring and rapid communication by the investigator to the sponsor may be appropriate. Such events may require further investigation in order to characterize and understand them. Depending on the nature of the event, rapid communication by the study sponsor to other parties may also be needed (e.g., regulators). Reference: CIOMS VI
The AEs will be coded using the current version of Medical Dictionary for Regulatory Activities (MedDRA; refer to https://www.meddra.org).	

14.3 Adverse Event Severity Grading Scale

Grade 1	Mild	Asymptomatic or mild symptoms; clinical or diagnostic observations only; no intervention indicated
Grade 2	Moderate	Minimal, local, or noninvasive intervention indicated; limiting age-appropriate instrumental activities of daily living (ADL)
Grade 3	Severe	Severe or medically significant but not immediately life-threatening; hospitalization or prolongation of hospitalization indicated; disabling; limiting self-care ADL
Grade 4	Life-threatening	Life-threatening consequences; urgent intervention indicated
Grade 5	Death	Death related to AE
Reference: Common Terminology Criteria for Adverse Events (CTCAE) version 5.0		

14.4 AE Attribution Scale

RELATIONSHIP	ATTRIBUTION	DESCRIPTION
	Unrelated	The AE is clearly NOT related to the intervention.

	ONSET trial Protocol	Date: 10/02/2026 Version: 1.1
---	-----------------------------	----------------------------------

Unrelated to investigational agent/intervention	Unlikely	The AE is doubtfully related to the intervention.
Related to investigational agent/intervention	Possible	The AE may be related to the intervention.
	Probable	The AE is likely related to the intervention.
	Definite	The AE is clearly related to the intervention.
Reference: NCI Guidelines: Adverse Event Reporting Requirements		

14.5 Reporting procedures for AE

Given that the only study-specific procedure is an on-treatment biopsy – a well-established diagnostic technique with a well-known and limited safety profile – a risk-adapted approach will be adopted for AE reporting. Only biopsy-related adverse events (AEs) will be collected and reported in the study Case Report Form (CRF).

Routine, non-related AEs associated with anticancer treatment or underlying disease will not be systematically recorded, as they are considered part of standard clinical management and will already be documented in the patient's medical record.

14.6 Reporting Procedures for SAE/ AESI

All Serious Adverse Events (SAEs) deemed related or possibly related to the on-treatment biopsy must be reported promptly to the Sponsor/Authorized Representative and the Ethics Committee, following institutional and regulatory timelines. Examples of biopsy-related SAEs that require immediate reporting include:

- severe bleeding requiring transfusion or surgical intervention,
- biopsy-related infection requiring hospitalization or intravenous antibiotics,
- any event leading to prolonged hospitalization, permanent damage, or death.

SAEs clearly attributable to the underlying malignancy or standard anticancer therapy (e.g., disease progression, treatment-related toxicities, hospitalization for chemotherapy complications) will not be reported as study SAEs, as they are outside the scope of this protocol.

No AESIs have been predefined for this study, as no investigational product is used and the procedure's risk profile is well established.

14.7 Follow-up of AE / SAE / AESI

The Investigator should take all appropriate measures to ensure the safety of the patients. Notably, they should follow up on the outcome of any event (clinical signs, laboratory values, etc.) until resolution or until the event is considered stable.

In the case of any Serious Adverse Event, the patient must be followed up until clinical recovery is complete and laboratory results have returned to normal, or until progression has been stabilized. This may imply that follow-up will continue after the patient has left the study and that the Ethics Committee may request additional investigations.

14.8 Unblinding Procedures

Not applicable

15 DATA MANAGEMENT

15.1 Definition of source data and source documents

In this study, source documents consist exclusively of the participants' standard clinical records, including hospital charts and medical files, which are used to evaluate patient history and therapies received. The only additional study-specific source documents is the on-treatment biopsy procedure report. All data recorded in the Case Report Forms (CRFs) will be derived from these clinical records. Patient screen failures will also be documented in the source records, including the reason for ineligibility.

15.2 Documentation of data in Case Report Forms (CRFs)

All relevant study data for enrolled participants will be recorded in the CRFs (RedCap) by the principal investigator or an authorized delegate as soon as possible after collection. The investigator will verify completeness, accuracy, and compliance with ICH guidelines and institutional SOPs, signing and dating each CRF. Any missing data will be explained. Completed CRFs will remain at the study site, and for electronic CRFs, a copy of all pages will be securely stored locally.

15.3 Data Recording and Record Keeping

The investigator shall arrange for the retention of Essential Documents for the Conduct of a Clinical study (e.g., patient files, other source data, and the Trial Master File/Investigator Site File) after the completion or discontinuation of the study according to institutional procedures and applicable laws.

15.4 Data Protection

The Investigator undertakes to:

- use the data only for the foreseen analyses and within the limits established by the study and approved by the competent EC;
- store data in a secure network system;
- prohibit unauthorised third parties from accessing, even partially, data.
- guarantees to limit access to and processing of data only to its employees and collaborators who, upon appointment as an authorized person:
 1. need to process the data to carry out their work in relation to the study;
 2. have undertaken to maintain the confidentiality of the Data and any information deriving from it or that is communicated to them.

If, within the context of the Study, the Investigator needs to make use of its own suppliers, the latter undertakes to appoint these subjects as Data Processors/Responsabili dei Trattamenti with a specific agreement or other legal act suitable for this, before the start of any data processing by them, according to Regulation (EU) n. 2016/679, art. 28.

The Investigator also undertakes to adopt suitable measures to facilitate the exercise of the rights of the subject provided for by Regulation (EU) n. 2016/679, art. 15 – 22, including the rights of access, rectification, cancellation, limitation, opposition, and portability, within 30 days of receiving the relevant request. The Investigator will communicate the data outside OSR (the Data Controller/Titolare) in pseudonymized form, the Investigator will refrain from carrying out any activity that could identify the subjects to whom such data refer. In the event, however, that the data cannot be communicated in pseudonymized form by the Data Controller, the Investigator undertakes to adopt all necessary security and organizational measures aimed at protecting the confidentiality of the Data Subject.

16 STATISTICS

16.1 Given the translational and exploratory nature of this study, which is primarily focused on understanding the interactions between biology and clinical outcomes and on identifying potential predictive biomarkers employing high-throughput molecular and immunological profiling approaches, a formal statistical plan and power calculation are not applicable. The study is not designed for confirmatory hypothesis testing but for hypothesis generating. The number of participants has been defined to ensure scientific validity in high-throughput assays as those described, while minimizing patient burden and the use of biological material, in accordance with the principles of proportionality and ethical research conduct.

Description of Statistical Methods

Given the exploratory and translational nature of this study, which focuses on understanding tumor and immune dynamics and identifying potential predictive biomarkers, no formal

sample size calculation or hypothesis testing will be performed. Descriptive statistics will be used to summarize patient characteristics, sample collection, and molecular/immune profiling results. Continuous variables will be described using mean, median, range, and standard deviation, while categorical variables using frequency and percentage. To test association between categorical variables, chi-squared test will be applied while differences in continuous variables will be evaluated between different timepoints with t-test or Wilcoxon-Mann-Whitney, as appropriate with adjustments for multiple testing where relevant. Endpoints will be assessed at baseline, on-treatment, and at surgery, according to the time points specified in the study design. All analyses will be conducted using validated statistical software and all statistical tests, $p < 0.05$ will be considered statistically significant.

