Study Design	
This is an interventional translational, single-center study with a prospective, longitudinal cohort design based on serial tumor tissue collection and analysis for the identification of early tumor response biomarkers. Tumor samples will be obtained at three predefined time points: (i) prior to initiation of treatment (baseline biopsy), (ii) after Cycle 1 Day 1 (C1D1) of therapy, and (iii) at the time of surgery (surgical specimen). Among these, the only biopsy performed specifically for study purposes is the post-C1D1 biopsy; the baseline and surgical samples are collected as part of standard clinical management with no differences expected among the procedures. Analyses will focus on temporal molecular and histopathological changes across serial samples to characterize treatment-related tumor evolution.

Primary Objective To characterize the dynamic changes in tumor and immune cell populations in TNBC and to prospectively collect serial samples from high-risk luminal (ER+/HER2-) breast cancer patients.	Primary Endpoint Gene expression levels per single-cell and relative cell clustering (%)	Timepoints Pre-treatment, on-treatment (after first cycle of therapy), and post-treatment (surgery or residual disease)
Exploratory Objectives To correlate single-cell gene expression data with pCR and RD to identify predictive signatures of therapy response	Other pCR and RD	Timepoints Across all collected timepoints
Study Population	Adult female patients (≥ 18 years) with early breast cancer, triple negative or high-risk luminal (ER+/HER2) subtypes, candidate to receive SOC neoadjuvant chemo/immunotherapy	

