6. OBJECTIVES AND ENDPOINTS

Primary Objective	Primary Endpoint	Timepoints
-------------------	------------------	------------

To characterize the dynamic changes in tumor and immune cell populations in TNBC and to prospectively collect serial samples from high-risk luminal (ER+/HER2-) breast cancer patients	Gene expression levels per single-cell and relative cell clustering (%)	Pre-treatment, on-treatment (after first cycle of therapy), and post-treatment (surgery or residual disease)
Exploratory Objectives To correlate single-cell gene expression data with pCR and RD to identify predictive signatures of therapy response	Other pCR and RD	Timepoints Across all collected timepoints

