7. STUDY DESIGN

This exploratory interventional translational study investigates early breast cancer (EBC), focusing on triple-negative (TNBC) and high-risk luminal (ER+/HER2-) subtypes. By integrating single-cell RNA sequencing and spatial imaging analyses from serial tumor biopsies, the project aims to characterize tumor-immune interactions and identify predictive biomarkers of response or resistance to neoadjuvant chemo-immunotherapy⁹⁻¹².

The hypothesis of this study is that early molecular and spatial features identified at the single-cell level can predict therapeutic response or resistance in patients with early breast cancer, enabling adaptive, personalized treatment strategies that minimize overtreatment while maximizing efficacy. To test this hypothesis, we will conduct a translational study with a prospective longitudinal cohort design. The study is based on the existing retrospective experience with TNBC samples from the NeoTRIP trial⁹. Moreover we will prospectively collect serial tumor samples from high-risk luminal (ER+/HER2-) patients supported by the evidences already reported in the background. Two main patient cohorts will be included, TNBC and high-risk luminal breast cancer, and each participant will be followed from baseline (pre-treatment biopsy) through on-treatment (after the first cycle) to surgery (post-treatment or residual disease). The expected duration of participant involvement is approximately six months, according to the neoadjuvant treatment schedule. The study is monocentric, conducted at Ospedale San Raffaele, with collaborative contributions from SR-TIGET and Cambridge University for advanced single-cell and spatial analyses. No formal interim analysis is planned

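### The rank test named in Section 16.1 for differences between timepoints is an independent-samples test, and the t-test is not specified as paired, although the same patients are sampled serially

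*Protocol*

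**What the plan says.** The Synopsis describes a "prospective, longitudinal cohort design based on serial tumor tissue collection". Section 7 states that "each participant will be followed from baseline (pre-treatment biopsy) through on-treatment (after the first cycle) to surgery". Section 8.1 plans three timepoints for each of 20 TNBC and 35 luminal patients. Section 6 gives the primary objective as "To characterize the dynamic changes in tumor and immune cell populations in TNBC", together with serial collection in the luminal cohort; the primary endpoint is "Gene expression levels per single-cell and relative cell clustering", the latter as a percentage.

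For analysis, Section 16.1 provides that "differences in continuous variables will be evaluated between different timepoints with t-test or Wilcoxon-Mann-Whitney", whichever is appropriate, with adjustment for multiple testing where relevant and p < 0.05 as the significance threshold. Chi-squared is assigned to association between categorical variables. The protocol nowhere mentions a paired test, a signed-rank test, a repeated-measures analysis or a mixed model.

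Sections 16.1 and 16.3 describe the study as exploratory and say that no formal hypothesis testing will be done. Section 13 limits single-cell sequencing of the post-treatment TNBC sample to patients with residual disease.

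**The concern.** The sentence in Section 16.1 is about timepoints, so its natural use is baseline against post-cycle-1, or either against surgery, in the same women. Wilcoxon-Mann-Whitney assumes that the two sets of values come from different subjects; the paired counterpart is the signed-rank test. The protocol's 't-test' carries no qualifier, so it may or may not be run paired. The words that leave a choice to the analyst choose between a parametric and a rank test; they do not bring the pairing back into the rank test.

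If the unpaired version is used on correlated data, its standard error is wrong: too large when the two values from one patient are positively correlated, too small when they are negatively correlated. Either way the 5% threshold is not what it claims to be. In the usual positive case, early changes are missed in a cohort of 20. The on-treatment biopsy is the only procedure done purely for research, and much of its value lies in the contrast with the same patient's baseline sample.

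**Working it through.** **Is there a figure to reproduce?** No. The protocol gives no effect size, SD or power; the sample size is the sum 20 + 35 = 55, set on practical grounds (Section 16.2). The check therefore sizes the consequence under stated assumptions.

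**Inputs from the protocol.** 20 TNBC patients with serial samples (8.1); threshold 0.05 (16.1). Fewer than 20 patients at the third TNBC timepoint, number not given (13).

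**Assumptions.** Two-sided testing; one summary value per patient per timepoint; bivariate normal values with equal SD σ; within-patient correlation ρ from -0.2 to 0.7; shifts of 0.5 to 1.0 SD; 10 patients with residual disease for the surgical comparison.

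**Size of the unpaired test.** The unpaired test assumes that the variance of the mean difference is 2σ²/n. With the same patients at both timepoints it is 2σ²(1-ρ)/n. The large-sample type I error is therefore 2[1 - Φ(1.96/√(1-ρ))]. For ρ = 0.5: 1.96/√0.5 = 2.77, which gives 0.0056.

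| ρ | Formula | Simulated unpaired t, n=20 | Simulated Mann-Whitney, n=20 |
|---|---|---|---|
| -0.2 | 0.074 | 0.076 | 0.073 |
| 0 | 0.050 | 0.052 | 0.050 |
| 0.3 | 0.019 | 0.022 | 0.023 |
| 0.5 | 0.006 | 0.007 | 0.009 |
| 0.7 | 0.0003 | 0.001 | 0.001 |

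The paired t-test and signed-rank test stayed between 0.046 and 0.053 throughout (20,000 simulated trials per setting).

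**Power, n=20.**

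| ρ | Shift 0.5 SD: Mann-Whitney vs signed-rank | Shift 0.66 SD: unpaired t vs paired t | Shift 1.0 SD: unpaired t vs paired t |
|---|---|---|---|
| 0.3 | 29% vs 42% | 54% vs 66% | 91% vs 95% |
| 0.5 | 27% vs 55% | 54% vs 80% | 94% vs 99% |
| 0.7 | 24% vs 76% | 56% vs 95% | 97% vs 100% |

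The 0.66 SD shift is not neutral. It is the effect that a paired t-test on 20 patients detects with 80% power, in units of the SD of the difference. That SD is σ√(2(1-ρ)), which equals σ at ρ = 0.5, hence the 80% in the middle row. The 1.0 SD column shows how the gap closes when the effect is large.

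**Cost of pairing when it is not needed.** At ρ = 0 and 0.66 SD, n=20, power is 53% unpaired and 51% paired, a loss of about 2 points.

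**Surgical comparison, 10 pairs assumed, shift 0.8 SD, ρ = 0.5.** Unpaired t 37% vs paired t 62%; Mann-Whitney 32% vs signed-rank 54%.

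**What happens if cells are the unit.** The figures above do not apply if single cells are pooled. Take, as an assumption, 20 patients, 100 cells per sample, total variance 1 and an intraclass correlation of 0.1, half of it shared between a patient's two timepoints. The true variance of the mean difference is 2 × (0.05 + 0.9/100)/20 = 0.0059. An unpaired cell-level test assumes 2 × 1/2,000 = 0.0010. The SD ratio is √5.9 = 2.43, and 2[1 - Φ(1.96/2.43)] is about 0.42. The error then runs the other way, which is why the remedy should fix the unit as well as the pairing.

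**The case against.** **Both named tests ignore the pairing.** A reader might infer this, but the text does not support it. An unqualified t-test can be run paired and still comply with Section 16.1. Only the rank test is unambiguously unpaired. The point about the rank test stands, and it matters because a rank test is a likely choice for cell percentages in 20 patients.

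**The primary conclusions are invalid, or the longitudinal design is lost.** Neither follows. The study defines no primary contrast and disclaims formal hypothesis testing. Sampling is unaffected, each participant has a unique code (11.3), and the data can be analysed as pairs at any time. What remains is that Section 16.1 names tests and a p < 0.05 threshold, so the choice of test decides which changes are put forward.

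**The error is always conservative.** It is not. That holds for positive correlation and patient-level values. The documents quantify neither the correlation nor the unit of analysis. Positive correlation is plausible for repeated biopsies of one tumour, but it is an assumption.

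**The analysis plan can settle it.** A separate plan may exist and name paired tests. It would then have to depart from the protocol's own sentence, so the sentence still needs correcting.

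**The categorical tests have the same fault.** A reader might extend the point to chi-squared and ask for McNemar's test. Section 16.1 assigns chi-squared to association, not to change over time, so no such error is stated.

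**A mixed model would recover patients without a surgical sample.** In TNBC the post-treatment sample is sequenced only when residual disease is present. Its absence in complete responders is the outcome itself, not incidental missing data, and a model that filled in tumour values for them would be extrapolating.

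**Conclusion.** The point holds in limited form. Section 16.1 names an independent-samples rank test, and a t-test not specified as paired, for comparisons between serial samples from the same patients. With patient-level values, n=20, a 0.66 SD shift and correlations of 0.3 to 0.7, the unpaired t-test gives up about 12 to 39 points of power (66 - 54 and 95 - 56), and its true level is about 2% to 0.1%. The loss shrinks to 3-5 points at 1.0 SD and disappears at zero correlation; at -0.2 the unpaired test rejects about 7% of the time under the null. Correlations, shifts and the number of residual-disease cases are all assumptions, since the protocol gives none.

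The consequence is a distorted list of candidate changes in a hypothesis-generating study. No confirmatory claim and no patient's treatment depends on it. It should be fixed, because the sentence serves the primary objective and the correction is nearly free, but it does not undermine the study.

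**What to change.** Replace the continuous-variable sentence in Section 16.1 with wording to this effect:

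- Differences between two timepoints are tested on patient-level summary values (for example cluster percentage, or mean expression per patient and sample) with a paired t-test or Wilcoxon signed-rank test.
- Wilcoxon-Mann-Whitney, or an unpaired t-test, is used only for comparisons between different patients, such as pCR against residual disease.
- In TNBC, comparisons with the surgical sample apply to patients with residual disease only.

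A mixed model with a patient random effect is optional for the three timepoints together, but should not be used to infer surgical tumour values in patients with pCR. The chi-squared provision can stay as it is.

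The cost is a few lines of protocol text, with no extra patients, samples or data. The statistical downside is about 2 points of power at n=20 if the within-patient correlation is zero. At 10 pairs and a 0.8 SD shift it is about 3 points for the t-test (39.6% vs 36.2%) and 5 for the rank test (35.4% vs 30.2%).

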16.2 Sample Size Determination

The sample size has been determined based on practical considerations and the objectives of generating hypothesis-generating data. We plan to prospectively enroll a total of 55 patients, including 20 with TNBC and 35 with high-risk luminal breast cancer to conduct an exploratory proof-of-concept study. Based on the expected pCR rate at surgery and the early response to treatment at cycle 1, This project will leverage collaborations with Cambridge University (UK) for imaging mass cytometry (IMC) analyses and SR-TIGET for single cell-RNA sequencing experiments, which may allow expansion of the case series. Descriptive statistics and exploratory analyses will be conducted, applying appropriate methods to account for multiple testing and to summarize patient characteristics and molecular data.

All patients data and biological samples that need to be shared with collaborators will be pseudo-anonymized according to Institutional procedures and will be shared only after a specific agreement between San Raffaele Hospital and the research center.

